4.6.4. Patient Narratives

The following are “notable” events, from start of study drug through end of study participation (or data cutoff for the submission if earlier):

- deaths
- SAEs
- permanent discontinuations of study treatment due to AEs, and
- pregnancy.

Patient narratives (patient-level data and descriptive paragraph) will be provided for participants in the enrolled population with at least 1 notable event.

4.6.5. Special Safety Topics

For AESI or special safety topics, the counts and percentages of participants will be summarized by treatment and PT with decreasing frequency. Individual participant-level data may be presented. Displays with individual patient-level data may be created using various formats such as a customized listing and/or a customized graphical patient profile. Adverse events of special interest are defined in each section of special safety topics, where applicable. Listing will be generated for each AESI.

4.6.5.1. Exocrine Pancreas Safety

4.6.5.1.1. Pancreatic Enzymes

Observed pancreatic enzyme data (p-amylase and lipase) will be summarized by treatment. The counts and percentages of participants with maximum postbaseline pancreatic enzyme value exceeding the following thresholds will be provided by baseline pancreatic enzyme value (\leq ULN, $>$ ULN), and postbaseline: $\leq 1 \times$ ULN, (> 1 to ≤ 3) \times ULN, (> 3 to ≤ 5) \times ULN, (> 5 to ≤ 10) \times ULN, $> 10 \times$ ULN.

An MMRM analysis will be used to analyze each pancreatic enzyme with a log transformed (postbaseline measure/baseline measure) response variable and treatment, nominal visit, treatment-by-nominal visit interaction as fixed effects.

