### 9.4. Statistical Analyses

#### 9.4.1. General Considerations

Statistical analysis of this study will be the responsibility of the sponsor or its designee. Any change to the data analysis methods described in the protocol will require an amendment only if it changes a principal feature of the protocol. Any other change to the data analysis methods described in the protocol, and the justification for making the change, will be described in the statistical analysis plan (SAP) and the clinical study report (CSR). Additional exploratory analyses of the data will be conducted as deemed appropriate.

Unless otherwise noted, all tests of treatment effects will be conducted at a 2-sided alpha level of 0.05, and all confidence intervals will be given at a 2-sided 95% level. In statistical summaries and analyses, data will be analyzed as randomized.

Unless specified otherwise, efficacy analyses will be conducted using the efficacy analysis set (EAS), and safety analyses will be conducted using the safety analysis set (SS).

Unless specified otherwise, for analyses in the double-blind treatment period, baseline is defined as the last nonmissing data collected prior to or at randomization (Week 36); for analyses in the lead-in period, baseline is defined as the last nonmissing data collected prior to or at study entry (Week 0).

Summary statistics for continuous measures will include sample size, mean, SD, median, minimum, and maximum. The analysis model to make comparisons among treatment arms relative to continuous measurements assessed over time will be a mixed-model for repeated measures (MMRM) with terms of treatment, visit, treatment-by-visit interaction, stratification factors, and baseline measurement as a covariate. An unstructured covariance structure will model the relationship of within-patient errors.

The Kaplan-Meier method will be used for estimation of cumulative event-free survival rates over time, and Cox proportional hazards regression analysis will be used to compare hazard rates among treatments.

Summary statistics for categorical measures (including categorized continuous measures) will include sample size, frequency, and percentages. Logistic regression will be used to examine the treatment difference in binary efficacy outcomes if there is a need to adjust for covariates. Otherwise, Fisher's exact test will be used to examine the treatment difference in categorical outcomes.

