1.3. Study Design

Study GPHN is a Phase 3, multicenter, randomized, parallel-arm, double-blind, placebo-controlled, 88-week study that will investigate the impact of MTD of tirzepatide (10 mg or 15 mg QW), compared with placebo, on the maintenance of weight loss after an initial 36-week open-label tirzepatide lead-in treatment period, in study participants who do not have T2DM, and have obesity ($\text{BMI} \geq 30 \text{ kg/m}^2$) or are overweight ($\text{BMI} \geq 27 \text{ kg/m}^2$) with at least 1 weight-related comorbid condition, excluding diabetes mellitus.

Study GPHN will consist of 4 periods: a 2-week screening period; a 36-week open-label tirzepatide lead-in treatment period (including a 20-week dose-escalation period); a 52-week double-blind, placebo-controlled treatment period; and a 4-week safety follow-up period. The study participants will be randomized in a double-blind 1:1 ratio (tirzepatide MTD QW or placebo) at the end of the open-label lead-in treatment period. Assignment to treatment groups will be determined by a computer-generated random sequence using the IWRS. An upper limit of 70% enrollment of women will be used to ensure a sufficiently large sample of men.

The randomization will be stratified by country, sex (female, male), tirzepatide MTD dose at 36 weeks (10 mg versus 15 mg), and percent weight loss at 36 weeks (<10% versus $\geq 10\%$). Where necessary to be included as a stratification factor, countries with fewer than 10 randomized participants will be pooled into 1 category (pooled country).

Abbreviations: MTD = maximum tolerated dose; QW = once weekly; (T) = telephone visit.

Figure GPHN.1.1. Illustration of study design for Clinical Protocol I8F-MC-GPHN.

The details about the overview of study periods and study visits can be found in Study GPHN protocol Section 4. Details of the unique visits not displayed in [Figure GPHN.1.1](#) are provided below.

Visit 99

Visit 99 is only applicable to participants who discontinue the double-blind study treatment prematurely (after Week 36 and before Week 88) and decline to complete the remaining scheduled study visits. These participants will be asked to return for Visit 99 at 88 weeks ± 7 days. This visit is critical to ensure complete data collection for the primary body weight endpoint.

Early Discontinuation of Treatment Visit

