The mean change from baseline differences among treatments at all scheduled visits will be assessed via an MMRM using REML. Unless specified otherwise, if the safety parameter is assessed at 88 weeks, then the model will include country/pooled country, sex, tirzepatide MTD dose at randomization, percent weight loss at randomization (<10% and $\geq 10\%$), treatment group, visit and treatment-by-visit interaction as fixed effects, and baseline value of the safety parameter as a covariate. To model the covariance structure within participants, the unstructured covariance matrix will be used. If this model fails to converge, the covariance structures specified in

Section 4.3.2.2 will be tested in order until convergence is met. If the data does not warrant the MMRM model, then ANCOVA model will be conducted.

For selected parameters, time-to-first-event analysis via the Cox-proportional hazards model may be conducted. Participants without the event will be censored at the end of study participation.

For participants experiencing the event, the “time-to-first-event” will be the time (in weeks) from first dose or randomization (depends on the event of interest and analysis feature, eg, for time to study discontinuation, time from first dose might be used; for time to AE during double-blind treatment period, time from randomization might be used) to first occurrence of the event.

Where necessary, the rate of events will be analyzed using a generalized linear mixed-effects model assuming the number of events follows a negative binomial distribution and with treatment as a fixed effect. The logarithm of days during the double-blind treatment period will be adjusted as an offset to account for possible unequal treatment duration of follow-up between participants.

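### The pancreatic enzyme MMRM analyses the log ratio to baseline without a baseline covariate or the stratification factors, unlike the SAP's own default safety model

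*SAP*

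**What the plan says.** SAP 4.6.5.1.1 (Pancreatic Enzymes) gives each enzyme an MMRM with a "log transformed (postbaseline measure/baseline measure) response variable" and "treatment, nominal visit, treatment-by-nominal visit interaction as fixed effects". Baseline appears only as the denominator of the response. No covariate is named, and none of the four randomization factors (country, sex, 10 mg or 15 mg dose group, lead-in weight loss below 10% or at least 10%) is listed.

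SAP 4.6 sets the default for mean-change safety analyses. It begins "Unless specified otherwise, if the safety parameter is assessed at 88 weeks, then the model will include country/pooled country, sex", continues with dose group and percent weight loss, and ends "treatment group, visit and treatment-by-visit interaction as fixed effects, and baseline value of the safety parameter as a covariate". Protocol 9.4.1 describes its general MMRM for continuous measures in the same way: "terms of treatment, visit, treatment-by-visit interaction, stratification factors, and baseline measurement as a covariate".

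**The concern.** The enzyme model leaves out every adjustment term that the default carries, without explanation. A ratio to baseline may look as if it already deals with baseline, but it forces a slope of exactly 1 on the log scale. When the true slope is below 1, the log ratio carries extra noise from the baseline measurement. In a given trial that noise appears as chance baseline imbalance, passed into the arm contrast through regression to the mean.

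What is at stake is precision. The comparison of enzymes that the SAP places beside adjudicated pancreatitis, an adverse event of special interest, would have a wider interval than the data support. Stratified randomization followed by an analysis without the strata may lose some further precision.

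**Working it through.** **Does anything in the documents explain the shorter model?**

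- *The log scale does not.* SAP Table GPHN.4.3 log-transforms fasting insulin and lipids and keeps all stratification factors plus the baseline value as a covariate. SAP 4.6.5.11 log-transforms the urine albumin-to-creatinine ratio and lists no reduced model, so the 4.6 default applies.
- *The list of changes does not.* Protocol 9.4.1 says that changes to its methods will be described in the SAP and CSR with their justification. SAP 4.9 covers only the two weight-reduction thresholds promoted to key secondary.
- *The visit structure does not.* In the Schedule of Activities, lipase and pancreatic amylase are marked at Visits 1, 5, 8, 11 and 24, early discontinuation and Visit 801. After randomization at Visit 11, the only scheduled on-treatment measurement is Week 88. Repeated measures therefore add little, and the model is close to an unadjusted two-group comparison of log ratios.

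**Size of the loss.** The plan states no figure for this model, so there is none to reproduce.

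Inputs: 1:1 randomization (Protocol 9.2); rho, the correlation between log baseline and log Week 88 value, which the documents do not give and is assumed here between 0.3 and 0.9; and equal variance s² at both times, also assumed.

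- Variance per participant of the log ratio: s² + s² − 2·rho·s² = 2(1 − rho)s².
- Residual variance with log baseline as covariate: (1 − rho²)s².
- Variance ratio, adjusted to unadjusted: (1 − rho²) / [2(1 − rho)] = (1 + rho)/2.
- Standard error ratio: sqrt((1 + rho)/2).

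| rho (assumed) | Variance ratio | SE ratio | SE reduction |
|---|---|---|---|
| 0.3 | 0.65 | 0.806 | 19% |
| 0.5 | 0.75 | 0.866 | 13% |
| 0.7 | 0.85 | 0.922 | 8% |
| 0.8 | 0.90 | 0.949 | 5% |
| 0.9 | 0.95 | 0.975 | 2.5% |

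A simulation with 225 per arm (300 × (1 − 0.25), using the plan's dropout assumption) and 3,000 replicates gave variance ratios of 0.743, 0.844 and 0.957 at rho 0.5, 0.7 and 0.9, against 0.75, 0.85 and 0.95 from the formula. With no true effect, the mean estimated effect was about zero under both models, so neither is biased on average.

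**Chance imbalance.** For a given baseline difference between arms on the log scale, the unadjusted contrast shifts by −(1 − rho) times that difference; the adjusted contrast does not shift. This is not a second loss: 2(1 − rho) − (1 − rho²) = (1 − rho)², so the variance that adjustment removes is exactly the variance of that shift.

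**Unequal variances.** With baseline SD a and Week 88 SD b, the log-ratio variance minus the adjusted variance is (a² + b² − 2·rho·a·b) − b²(1 − rho²) = (a − rho·b)². This is never negative, so relaxing the equal-variance assumption changes the size of the gain but not its direction (apart from the single degree of freedom spent on the slope).

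The gain from the stratification factors cannot be computed from the documents.

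**The case against.** The strongest reply is that the default yields to any more specific text, and 4.6.5.1.1 is more specific. A log ratio in a reduced MMRM is a valid randomized comparison, so the choice concerns efficiency and is neither an error nor a contradiction. That stands, and it is why the point is minor. It does not supply a reason for giving up the precision.

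Second, 4.6.5.1.1 lists fixed effects only, whereas 4.6 names baseline separately as a covariate. The section does not exclude a covariate, so the default one may have been meant to carry over. This is a fair reading for baseline and a weaker one for the stratification factors, which 4.6 lists among the fixed effects. If it is right, the text is ambiguous, and the same edit resolves it.

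Third, the analysis is supportive. Pancreatitis as an event of special interest is defined by adjudication, not by this model. Protocol 8.3.2.2 itself gives serial enzyme values little predictive use in asymptomatic patients. The threshold table in 4.6.5.1.1 is already split by baseline at the upper limit of normal, and SAP 2.1 makes no multiplicity adjustment for safety. All of this limits the consequence and stands.

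Fourth, SAP 4.6 has a fallback: "If the data does not warrant the MMRM model, then ANCOVA model will be conducted". With one on-treatment visit it may well be used. But no covariates are listed for it, so it does not settle what the enzyme model contains.

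**Conclusion.** The concern holds as a minor, avoidable loss of precision. As written, the enzyme model omits the baseline covariate and the stratification factors that the SAP's default and the Protocol's general model include, and no reason is given. Adding log baseline would shorten the standard error by 19% to 5% for correlations of 0.3 to 0.8, and by about 2.5% at 0.9. These figures rest on an assumed correlation and equal variances on the log scale; the direction of the gain does not depend on equal variances. There is no bias on average, no type I error inflation and no strict contradiction, because the default allows exceptions. No figure can be given for the stratification factors.

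**What to change.** In SAP 4.6.5.1.1, add log(baseline enzyme) as a covariate, using the same baseline value as the denominator of the response, and the four stratification factors as fixed effects, as in SAP 4.6. The response can stay as it is: with log baseline in the model, the treatment contrast is the same whether the response is the log ratio or the log postbaseline value. State that the same terms apply if the ANCOVA fallback is used. If the reduced model is deliberate, say so and give the reason.

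The cost is one sentence in the SAP. The values are already collected, and trial conduct does not change.

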4.6.5.1.2. Pancreatitis Events

Summaries of adjudicated and investigator-reported pancreatic events will be provided by treatment. Detailed search criteria can be found in [Appendix 6](#).

Treatment-emergent adjudication confirmed pancreatitis will be considered as an AESI. Listing of participants with adjudicated pancreatitis may be provided if deemed necessary.

4.6.5.2. Gastrointestinal Adverse Events

4.6.5.2.1. Nausea, Vomiting, and Diarrhea

Summaries and analyses for incidence and severity of nausea, vomiting (including “vomiting” and “vomiting projectile”), diarrhea (including “diarrhea” and “diarrhoea”), and 3 events combined will be provided by each treatment group. Summary of the prevalence over time for

nausea, vomiting, and diarrhea will also be presented. Time to the first onset of nausea, vomiting, and diarrhea will be plotted.

4.6.5.2.2. Severe Gastrointestinal Events

Severe GI AEs (GI SOC) will be captured with AE-CRF form and serious cases will be captured with the SAE form. The PTs in the GI SOC from the most recent MedDRA version at the time of database lock will be used to identify GI AEs, and only the PTs with severe/serious cases will be considered as AESIs.

The counts and percentages of participants with severe/serious GI events will be summarized by treatment.

4.6.5.3. Hepatobiliary Disorders

4.6.5.3.1. Hepatic Events

Severe/serious hepatic events will be considered as AESI and summarized separately. The counts and percentages of participants with treatment-emergent potentially drug-related hepatic events will be summarized by treatment using the MedDRA PTs. Detailed searching criteria can be found in [Appendix 7](#).

4.6.5.3.2. Acute Gallbladder Disease

Events related to acute gallbladder disease will also be summarized by treatment groups by PT with decreasing frequency. Detailed searching criteria can be found in [Appendix 7](#).

Severe/serious acute gallbladder disease will be considered as AESIs and summarized separately.

4.6.5.3.3. Liver Enzymes

Common analyses for laboratory analyte measurements described in Section [4.6.3.3](#) are applicable for the liver enzyme-related measurements. This section provides additional analyses for liver enzymes.

The counts and percentages of participants with the following elevations in hepatic laboratory tests at any time during the double-blind treatment period and during double-blind treatment period including follow up period will be summarized between treatment groups:

- The counts and percentages of participants with an ALT measurement $\geq 3 \times$, $5 \times$, and $10 \times$ ULN for the central lab will be summarized for all participants with a postbaseline value and for subsets based on the following levels of baseline value:
 - participants whose nonmissing maximum baseline value is $\leq 1 \times$ ULN
 - participants whose maximum baseline is $>1 \times$ ULN, and
 - participants whose baseline values are missing.
- The counts and percentages of participants with an aspartate aminotransferase) measurement $\geq 3 \times$, $5 \times$, and $10 \times$ ULN for the central lab will be summarized for all patients with a postbaseline value and for subsets based on various levels of baseline, as described above for ALT.

- The counts and percentages of participants with a total bilirubin measurement $\geq 2 \times$ ULN for the central lab will be summarized for all participants with a postbaseline value, and for subsets based on the following levels of baseline values:
 - participants whose nonmissing maximum baseline value is $\leq 1 \times$ ULN,
 - participants whose maximum baseline is $>1 \times$ ULN, but $<2 \times$ ULN,
 - participants whose maximum baseline value is $\geq 2 \times$ ULN, and
 - participants whose baseline values are missing.
- The counts and percentages of participants with a serum alkaline phosphatase measurement $\geq 2 \times$ ULN for the central lab will be summarized for all participants with a postbaseline value, and for subsets based on various levels of baseline, as described for total bilirubin.

Maximum baseline will be the maximum nonmissing observation in the baseline period. The maximum postbaseline value will be the maximum nonmissing value from the postbaseline period. Planned and unplanned measurements will be included.

4.6.5.4. Hypoglycemia

The following categories in accordance with the American Diabetes Association position statement on glycemic targets (ADA 2020) will be defined in the database.

Glucose Alert Value (Level 1):

- Documented **symptomatic hypoglycemia** is defined as any time a participant feels that he/she is experiencing symptoms and/or signs associated with hypoglycemia, and has a PG level of <70 mg/dL (<3.9 mmol/L).
- Documented **asymptomatic hypoglycemia** is defined as any event not accompanied by typical symptoms of hypoglycemia, but with a measured PG <70 mg/dL (<3.9 mmol/L).
- Documented **unspecified hypoglycemia** is defined as any event with no information about symptoms of hypoglycemia available, but with a measured PG <70 mg/dL (<3.9 mmol/L).

Documented Clinically Significant Hypoglycemia (Level 2):

- Documented **symptomatic hypoglycemia** is defined as any time a participant feels that he/she is experiencing symptoms and/or signs associated with hypoglycemia and has a blood glucose (BG) level of <54 mg/dL (<3.0 mmol/L).
- Documented **asymptomatic hypoglycemia** is defined as any event not accompanied by typical symptoms of hypoglycemia but with a measured BG <54 mg/dL (<3.0 mmol/L).
- Documented **unspecified hypoglycemia** is defined as any event with no information about symptoms of hypoglycemia available but with a measured BG <54 mg/dL (<3.0 mmol/L).

Severe Hypoglycemia (Level 3):

Severe hypoglycemia is defined as an episode with severe cognitive impairment requiring the assistance of another person to actively administer carbohydrate, glucagon, or other resuscitative actions. These episodes may be associated with sufficient neuroglycopenia to induce seizure or coma. Plasma glucose measurements may not be available during such an event, but neurological recovery attributable to the restoration of PG to normal is considered sufficient evidence that the event was induced by a low PG concentration.

Other hypoglycemia categories:

- Nocturnal **hypoglycemia** is defined as any hypoglycemic event that occurs between bedtime and waking.

If a hypoglycemic event meets the criteria of severe, the event would specifically be collected as an SAE. Serious hypoglycemia is defined by pharmacovigilance criteria and will also be captured with an SAE form.

To avoid duplicate reporting, all consecutive hypoglycemic events occurring within a 1-hour period will be considered to be a single hypoglycemic event.

Both the incidence (percent of participants experiencing ≥ 1 episode) and the rate (episodes/patient/year) of Level 2 or Level 3 hypoglycemia, and Level 3 hypoglycemia will be reported.

[figure not shown]
Severe/serious hypoglycemia will be considered as AESIs. The summaries of severe/serious hypoglycemia will be provided by treatment group. A listing of all events of severe/serious hypoglycemia may be provided, if deemed necessary. This listing will provide treatment, and clinical characteristics of the hypoglycemic event.

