### 8.3.2. Special Safety Topics

#### 8.3.2.1. Hypoglycemia

Upon ICF signing, all participants will be educated about signs and symptoms of hypoglycemia, how to treat hypoglycemia, and how to collect appropriate information for each episode of hypoglycemia. Hypoglycemia may be identified by spontaneous reporting of symptoms from participants (whether confirmed or unconfirmed by simultaneous glucose values) or by blood glucose (BG) samples collected during study visits.

All participants who develop diabetes during the study will be provided with glucometers. Participants without diabetes may be given glucometers to assist in the evaluation of reported symptoms consistent with hypoglycemia at the investigator's discretion. Participants receiving glucometers will be provided a diary to record relevant information (for example, glucose values, symptoms).

All hypoglycemic episodes will be recorded on a specific eCRF (Hypoglycemic Events eCRF) and should not be recorded on the AE eCRF, unless the event meets serious criteria. If a hypoglycemic event meets severe criteria (see definition below), it should be recorded as serious on the AE and SAE eCRFs, and reported to Lilly as an SAE. All posttreatment hypoglycemic events collected on the hypoglycemic eCRF will be considered as treatment-emergent and included in the analysis of incidence and rate of hypoglycemic events.

Investigators should use the following definitions and criteria when diagnosing and categorizing an episode considered to be related to hypoglycemia (the BG values in this section refer to values determined by a laboratory or International Federation of Clinical Chemistry and Laboratory Medicine blood-equivalent glucose meters and strips) in accordance with the 2020 American Diabetes Association position statement on glycemic targets (American Diabetes Association 2020):

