##### *Glucose Alert Value (Level 1):*

- **Documented symptomatic hypoglycemia** is defined as any time a participant feels that he or she is experiencing symptoms and/or signs associated with hypoglycemia and has a BG level of  $<70$  mg/dL ( $<3.9$  mmol/L).
- **Documented asymptomatic hypoglycemia** is defined as any event not accompanied by typical symptoms of hypoglycemia, but with a measured BG  $<70$  mg/dL ( $<3.9$  mmol/L).
- **Documented unspecified hypoglycemia** is defined as any event with no information about symptoms of hypoglycemia available, but with a measured BG  $<70$  mg/dL ( $<3.9$  mmol/L).

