4.9. Changes to Protocol-Planned Analyses

To provide data on efficacy of the investigational product that would be valuable to better inform clinical decisions in management of people living with obesity, protocol-planned objectives are changed as below.

Key secondary objectives:

- Moving percentage of study participants who achieve $>20\%$ body weight reduction at Week 88 from Visit 2 (Week 0) from exploratory endpoint to a key secondary endpoint.
- Moving percentage of study participants who achieve $>15\%$ body weight reduction at Week 88 from Visit 2 (Week 0) from additional secondary endpoint to a key secondary endpoint.

5. Sample Size Determination

Approximately 1000 participants will be screened and 750 participants enrolled into the 36-week open-label tirzepatide lead-in treatment period for approximately 600 participants to be randomized in a 1:1 ratio to tirzepatide MTD (300 participants) or placebo (300 participants).

The sample size determination assumes that evaluation of superiority of tirzepatide MTD to placebo will be conducted at a 2-sided significance level of 0.05 using a 2-sample t-test.

Additionally, a difference of at least 6% mean body weight percentage change from randomization (36 weeks) to 88 weeks between tirzepatide MTD and placebo, a common SD of 8%, and a dropout rate of 25% are assumed for statistical power calculations. Under the assumptions above, randomizing 600 participants in a 1:1 ratio to tirzepatide MTD (300 participants) and placebo (300 participants) provides more than 90% power to demonstrate superiority of tirzepatide MTD to placebo.

6. Supporting Documentation

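### The SAP's hypoglycemia incidence and rate leave out non-severe, non-serious episodes of 54 to <70 mg/dL and episodes without a glucose value, which the protocol says are analyzed, and the narrowing is not recorded

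*SAP*

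**What the plan says.** Protocol 8.3.2.1 (Hypoglycemia) sets the collection route: "All hypoglycemic episodes will be recorded on a specific eCRF (Hypoglycemic Events eCRF) and should not be recorded on the AE eCRF", with an exception for events that meet serious criteria. It then says what is analyzed: "All posttreatment hypoglycemic events collected on the hypoglycemic eCRF will be considered as treatment-emergent and included in the analysis of incidence and rate". No level is excluded. The same section accepts episodes identified from symptoms alone, with or without a simultaneous glucose value, as well as from glucose samples taken at visits. A severe episode must also be recorded as serious.

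The protocol defines three levels: Level 1 (glucose <70 mg/dL), Level 2 (<54 mg/dL) and Level 3 (severe, needing another person's help, with or without a measured glucose). SAP 4.6.5.4 repeats them and states that the categories "will be defined in the database". Its asymptomatic Level 1 category, for example, "is defined as any event not accompanied by typical symptoms of hypoglycemia, but with a measured PG <70 mg/dL".

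The outputs that follow are narrower. Incidence and rate are planned for "Level 2 or Level 3 hypoglycemia, and Level 3 hypoglycemia will be reported". The only other hypoglycemia output by arm is a summary of severe or serious events.

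Protocol 9.4.1 says that a change in analysis method too small to need an amendment is to be described, with its justification, in the SAP and the clinical study report. SAP 4.9 opens its list with "protocol-planned objectives are changed as below" and names only the moves of the 15% and 20% weight-loss endpoints.

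**The concern.** The protocol promises an incidence and rate analysis of everything on the hypoglycemia form, and the SAP delivers part of it. Normally the general adverse event tables would catch the rest. Here they cannot, because non-serious episodes are deliberately kept off the adverse event form. Sites are asked to record a class of episode for which no planned output gives a count by arm.

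What is at stake is the completeness of one safety display and the traceability of a departure from the protocol. No efficacy result depends on it.

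**Working it through.** Neither document states a hypoglycemia figure, so there is nothing to reproduce numerically. The check is to take each kind of episode that the form can hold and follow it through the planned outputs. The inputs are the form-routing rule and level definitions in Protocol 8.3.2.1, the outputs in SAP 4.6.5.4, and the adverse event tables in SAP 4.6.2.

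| Episode on the hypoglycemia form | Incidence and rate (SAP 4.6.5.4) | Severe/serious summary by arm | Adverse event form, hence TEAE tables |
|---|---|---|---|
| Severe (Level 3), with or without glucose | Yes, both lines | Yes | Yes, as serious |
| Serious but not severe | Only if <54 mg/dL | Yes | Yes |
| Neither, glucose <54 mg/dL | Yes, Level 2/3 line | No | No |
| Neither, glucose 54 to <70 mg/dL | **No** | **No** | **No** |
| Neither, no glucose value | **No** | **No** | **No** |

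Three steps lie behind the table.

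1. Level 1 has no lower bound in either document. An episode at, say, 50 mg/dL meets the Level 1 and the Level 2 definitions and is counted through Level 2. What is left out is therefore not Level 1 as a whole but the band from 54 to <70 mg/dL.

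2. An episode reported from symptoms alone has no glucose value, so it fits neither Level 1 nor Level 2. It counts only if it is severe. The protocol's analysis sentence still covers it, because it is on the form.

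3. Other planned outputs were checked for a substitute. SAP 4.6.3.6 plans low/normal/high shift tables for laboratory analytes, compared between arms by Fisher's exact test and including unscheduled measurements. Glucose is in the chemistry panel, so a low value in a laboratory sample can appear there. But those tables use the performing laboratory's limits, not 70 or 54 mg/dL, and they classify participants' samples rather than count episodes. Glucometer readings and symptom reports do not enter them. SAP 4.1 allows additional analyses as appropriate, which permits an all-episode count but does not plan one.

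The bottom two rows of the table are the gap.

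**The case against.** The best defense is that the protocol sentence sits in a data-collection section and mainly settles which events count as treatment-emergent. The protocol's statistical section (9.4.4.3) names only severe hypoglycemia as an event of special interest and leaves the details to the SAP. Reporting only clinically significant levels in people without diabetes is a defensible choice, and SAP 4.9 is worded as a list of changed objectives, not of safety tables.

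Part of this stands. The choice may well be reasonable, and the departure is small. But the protocol sentence does more than define treatment emergence: it also places the events in the incidence and rate analysis. Special-interest status governs a different set of displays. If 4.9 is not the natural place for the explanation, Protocol 9.4.1 still calls for one, and none of the SAP sections on hypoglycemia, general safety methods or changes gives it. The text as read has an omitted figure just after the SAP's output sentence; its content cannot be checked, and nothing refers to it as an all-episode output.

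Two stronger readings are tempting. A reader might infer that no Level 1 event is ever compared between arms. The documents do not support that: episodes <54 mg/dL enter through Level 2, serious ones through the severe/serious summary, and some low values through the laboratory shift tables.

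A reader might also infer that the narrowing costs substantial power to detect a difference. Neither document gives an incidence, and the answer follows entirely from the gap one assumes. With 300 per arm and a two-sided Fisher test at 0.05, assumed all-episode incidences of 3% vs 8% give 73% power and 5% vs 12% give 85%, but 3% vs 4% gives 7% and 5% vs 6% gives 6%. Nor do the documents show what share of episodes would fall between 54 and 70 mg/dL.

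**Conclusion.** The discrepancy holds in a limited form. Followed as written, the SAP gives no planned episode incidence or rate by arm, and no TEAE entry, for non-severe, non-serious episodes of 54 to <70 mg/dL or for non-severe, non-serious episodes without a glucose value. The protocol says both are analyzed, and the SAP does not record or justify the difference.

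The number of episodes involved is unknown. The conclusion assumes only that the protocol's analysis sentence means what it says and that sites follow the form-routing rule. It is a minor reconciliation point in safety reporting. The primary and key secondary conclusions do not depend on it, and the more serious hypoglycemia outcomes are already covered.

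**What to change.** In SAP 4.6.5.4, add incidence and rate by treatment group for all posttreatment events on the hypoglycemia form, over the same window as the existing lines. Show documented episodes <70 mg/dL and episodes without a glucose value as separate rows; a row limited to documented episodes would still fall short of the protocol. Use the methods already in SAP 4.6: Fisher's exact test for incidence and the negative binomial model for rate. Keep the Level 2/3 and Level 3 lines as the clinically important ones.

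If the sponsor prefers the narrower reporting, the alternative is to state and justify the restriction in SAP 4.9 and the clinical study report, as Protocol 9.4.1 asks.

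The cost is a few rows in a planned table. The form data are already collected, and the glucose categories are already to be derived. The small downside is that mild or asymptomatic events will appear in the report.
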